4.1. Treatment Design

We have selected transdermal estradiol because it avoids the first-pass metabolic effects of oral estrogen, and thereby creates more stable, premenopausal follicular phase E2 levels than oral and a physiologic profile of E2 relative to its metabolites. ^{17–19}TE2 also has a superior safety profile than oral estrogen. ^{20–22} We have selected the 0.1 mg/day dose because that is the dose that prior RCT research has shown to be effective in treating perimenopausal women with current depression ²⁷ and the dose we have used in our previous RCTs involving TE2 in which we found it to be both safe as well as effective in reducing depressive symptoms and in preventing the emergence of depressive episodes in perimenopausal women, particularly in those with recent life stress. ⁷

Additionally, we chose a 7-day system because a 7-day transdermal system provides more stable levels and better compliance than twice weekly patches.²³The adhesive layer of the matrix in Climara® patches continuously releases E2, which is transported across skin leading to sustained E2 levels.¹⁸

4.2. Experimental Design

We have selected a within subjects, double-blind, cross-over design because of the greater statistical power over a between subjects RCT and to minimize bias.

Participants are randomized (1:1), without stratification, to order of TE2 versus transdermal placebo. Participants will receive either three weeks of transdermal E2 (0.1 mg/day) or three weeks of transdermal placebo as their first condition (Condition 1) and the other treatment (active E2 or placebo) as their second condition.

4.3. Measurement Design

Table 1. Variables of interest: their occasions of evaluation, their uses for the aims, their roles in the study

Variables within Domains	Scale ¹	Visits ²	Aims	Main Roles
Identifiers				
Participant ID	nominal	all	all	identifier
Screening Profile				
systolic blood pressure (SBP)	mmHg	0, 5-7, 11-13	N/A	screening and safety
diastolic blood pressure (DBP)	mmHg	0, 5-7, 11–13	N/A	screening and safety

body mass index (BMI)	kg/cm ²	0, 7, 13	N/A	screening and safety
age	decimal yrs	0	N/A	screening
Life Events Survey	binary	0	N/A	screening
Psychiatric history	categorical	0	N/A	screening
Medical and cancer history	binary	0	N/A	screening
Reproductive Stage	binary	0	all	screening
Research Lab Assays				
Urinary E1G	pg/ml	1-4, 7, 13	Aim 1	predictor
EEG (theta and beta) oscillatory activation	dB	4, 7, 13	all	primary outcome
Patient-Reported Outcomes				
Daily self-reported irritability	continuous	1 – 13	all	primary outcome
Behavioral inhibition/Activation Scale (BIS/BAS)	continuous	4, 7, 13	Aim 2	secondary outcome
Frustration to non-Reward Scale	continuous	4, 7, 13	Aim 2	secondary outcome
Green Climacteric Scale	continuous	0, 4, 7, 13	all	covariate
Pittsburgh Sleep Quality Index	continuous	0, 4, 7,13	all	covariate
Safety Monitoring				
AEs and SAEs documentation	events	0, 4-13	N/A	safety monitoring

¹Units of measurement or the scale.

Screening Measures:

Blood pressure will be taken at baseline to confirm eligibility (< 160/100 mmHg) based on a minimum of three stethoscopic blood pressures taken by a trained research staff member. Participants will be seated comfortably for a minimum of five minutes prior to the first reading with arm supported on a table. Assessments will be at least one minute apart. A mean systolic and diastolic pressure (SBP and DBP) will be derived based on the three readings. Participants must have a resting SBP <160 and a resting DBP <100 mmHg to continue in the research. The same BP protocol will be used at study visit 5-7 and 11-13 to ensure the participant remains normotensive.

Body Mass Index will be derived based on height and weight measured by a research assistant in the laboratory using the Health-o-meter (Professional) scale. BMI will be calculated using the formula: weight in kg/height in m²

Age will be determined by self-report.

Reproductive Stage will be initially determined by phone and confirmed in the enrollment session based on self-report of bleeding patterns.

Psychiatric History will be determined by in-person interview using the Mini International Neuropsychiatric Interview (MINI) screens. Research staff will be trained by [name] to conduct the interview using the MINI training protocol that is used in [name] laboratory. All MINIS will be recorded, and [name] will review each MINI with the research staff member who conducted the interview to determine a consensus diagnosis. The audio recordings will be reviewed when needed to arrive at the diagnosis.

The Life Events Survey^{32,33}empirically modified to assess only those events that are moderate to severely stressful ("very stressful"), 34–36 will be used to confirm very stressful life events in the preceding 6 months. These include: divorce/separation, serious illness/death of close family member/friend, major financial problems, assault, life threat,

² Study Visits: 0 = enrollment; 1-4 = baseline phase; 5-7 = Condition 1; 8-10 = washout phase; 11 - 13 = Condition 2; 14 = Prometrium follow-up

personal or close relative's arrest for a serious crime. We will require 1+ very stressful life event (60% of our prior perimenopause samples). Other stressful life events (e.g., new job, major move, disagreements) are also assessed. We will administer this scale at the enrollment visit to confirm the presence of 1+ recent very stressful life event.

Outcome Variables:

The following questionnaires will be administered using the REDCap platform and associated participant MyCap app.

We will administer the Inventory of Depression and Anxiety Symptoms (IDAS)³⁷ at enrollment. This 64-item survey assesses ill temper (i.e., irritability), dysphoria, panic, social anxiety, appetite, lassitude, suicidality, well-being, traumatic intrusions, and insomnia. The IDAS has excellent psychometric properties and is validated in reproductive mood disorders.³⁷ Symptoms items for each scale are rated 1 (not at all) to 5 (extremely). The total IDAS score may range from 64 - 320 reflecting general level of psychological distress. Clinical cut points with diagnostic predictability have been established for Major Depressive Disorder (score \geq 32.5), Panic Disorder (score \geq 37.5), Post Traumatic Stress Disorder (score \geq 37.50), and Generalized Anxiety Disorder (score \geq 35.5).

We will administer the Center for Epidemiologic Studies Depression Scale (CES-D) weekly throughout the study. The total CES-D score may range from 0–60 reflecting level of depressive symptoms. A clinical cutpoint for Major Depressive Disorder has been established (score ≥16). We will monitor the weekly CES-D submissions and use scores at these levels to warrant follow-up by [name] or [name] to assess psychological distress and determine if the participant is able to continue in the study.

The **5-item ill temper scale of the IDAS will be the primary measure of irritability** and will be used at enrollment to ensure at least moderate levels of irritability, and daily to examine associations with E1G variability and EEG measures. **We will require an ill temper score of >10** (range 5-25), consistent with [name] preliminary data showing perimenopausal depressed women with levels of 11 on this scale are responsive to TE2.

The Behavioral Inhibition/Behavioral Activation Systems (BIS/BAS) 38 (RDoC Matrix) is comprised of 20 items. Respondents answer with a 1 – 4 scale (the statement is 1 = very true for me vs. 4 = very false for me). Lower scores reflect more agreement with the statement. This survey has five subscales that assess:

- 1) Behavioral activation (BAS, impulsivity) five item subscale with scores ranging from 5 20
- 2) Reward Responsiveness five item subscale with scores ranging from 5 20
- 3) Fun Seeking four item subscale with scores ranging from 4 16
- 4) Behavioral inhibition (BIS, anxiety) seven item subscale with scores ranging from 7 28.

We also include the 5-item $\frac{\text{Frustrative Non-reward Responsiveness Subscale}}{\text{Mon-reward Responsiveness Subscale}}$ (RDoC Matrix) to quantify approach motivation following FNR. This subscale is imbedded in the BIS/BAS instrument with lower scores reflecting greater frustration to non-reward. The scores range from 5-20.

We will administer these scales immediately before the two EEG tasks designed to activate threat/anxiety (the Dot Probe task) and frustration to non-reward (the Affective Posner Paradigm) at baseline Visit 4 and again at end of Condition 1 (Visit 7) and Condition 2 (Visit 13).

EEG Data Acquisition and Processing. A 32-channel actiCAP will be positioned according to the 10-20 system, with a Brain Products actiCHamp Plus amplifier. Preprocessing and analysis of EEG data will be performed using custom MATLAB scripts and the EEGLAB processing toolbox. EEG will be digitally re-referenced to the average reference, high pass filtered at 1.0 Hz, and epoched from -1 to 2 seconds to accommodate time-frequency analyses. EEG epochs containing amplitudes >100 μV at any scalp electrode with abnormally distributed data will be rejected. All cleaned, epoched data will be loaded into an EEGLAB STUDY mechanism to compute the time-frequency transform using the 'newtimef' 3-cycle wavelet function to yield Time X Frequency spectrograms. Theta (4-8Hz) and beta (13-30Hz) will be extracted from the pre-computed matrices at frontal (Fz) and parietal (Pz) midline electrodes.

E1G Assessments. We will use the same E1G assay and methods as Gordon et al,¹ who showed that variability in urinary E1G reliably identified perimenopausal women for whom *changes* in E1G predicted depression symptom severity. Week-to-week changes in E1G also differentiated women based on the direction of E1G change (i.e., increasing vs. decreasing levels) and symptom severity. The first morning voided urine will be used for measuring E1G, reflecting an integrated measure of overall E1G level from the previous day, and correlating very highly with serum E2 (r= 0.93).⁴0 At the end of each collection week, research staff will retrieve samples (stored in home freezer) and bring to our lab for storage at -80°C. Urinary E1G is not affected by the repeated freezing and thawing of specimens,⁴0 E1G will be assayed using an enzyme immunoassay (Arbor Assays, Ann Arbor, MI), with sensitivity at < 22.5 pg/mL. The specificity is high, with £ 0.1% cross-reactivity with similarly structured compounds, though cross-reactivity with E2 is higher at 5%. Since this research is focused on within person variation and we are using E1G as an indicator of E2 serum levels, any cross reactivity with E2 will not affect interpretability of our findings. The intra-assay variability = 4-6% and the inter-assay variability = 4-7%. Although there is little evidence to date that sensitivity to progesterone is a risk factor for affective impairment in the MT,¹ pregnanediol-3-glucuronide (PDG; a metabolite of progesterone) is assessed simultaneously with E1G and can be used as a covariate in analyses.

Control Variables:

The Pittsburgh Sleep Quality Index (PSQI) 41 is comprised of 19 self-rated items and five questions rated by the bed partner if one is available. Only self-rated questions are included in the scoring. The 19 self-rated items are combined to form seven "component" scores, each of which has a range of 0-3 points. In all cases, a score of 0 indicates "no difficulty", while a score of 3 indicates "severe difficulty" The seven component scores are then added to yield a global scores with a range of 0-21, 0 indicating 'no difficulty' and 21 indicating severe difficulties in all areas.

The components are: Subjective Sleep Quality, Sleep Latency, Sleep Duration, Habitual Sleep Efficiency, Sleep Disturbances, and Use of Sleep Medication.⁴¹

This survey will be measured at enrollment (Visit 0) and again at the end of Baseline (Visit 4) and each Condition (Visits 7 and 11) to be used as covariates in the model to confirm (or refute) that beneficial changes in outcomes due to TE2 cannot be explained by changes in perceived sleep quality.

The Greene Climacteric Scale 42 is a 21 item survey comprised of six subscales. Respondents indicate the degree to which they are bothered currently by symptoms on a 0 (not at all) to 3 (extremely) scale. The subscales are: measuring general psychological ii items), Anxiety (six items), Depression (5 items, score ranging from 0 – 15), somatic symptoms (7 items, score ranging from 0 – 21), vasomotor symptoms (2 items, score ranging from 0 – 6), sexual interest (1 item, score ranging 0 – 3) $^{43-45}$

This survey will be administered at enrollment (Visit 0) and again at the end of Baseline (Visit 4) and each Condition (Visits 7 and 11) to be used as covariates in the model to confirm (or refute) that beneficial changes in outcomes due to TE2 cannot be explained by changes in perceived sleep quality or menopausal symptoms (subscales somatic and vasomotor).

5. Study Participants

5.1. Numbers of Participants

Number to be screened: N £ 135Number to be enrolled: N = 50

Up to 135 individuals will be screened. Based on our prior experience with perimenopausal women and intervention studies involving transdermal E2, we estimate that 40% will fail the medical screening for TE2 eligibility, and an additional 20% will not be interested in participating.

It will be necessary to enroll 50 perimenopausal women because our prior experience also suggests that 30% (n=15) will not meet eligibility for TE2 upon further screening, yielding about 35 eligible for the randomized, cross-over study. We conservatively account for 15% (n =5) withdrawal following randomization, yielding 30 women who complete the protocol

Since this is a cross-over study design, all enrolled women will receive both the active TE2 condition and the placebo TE2 condition.

Recruitment: Participants will be recruited through the Menopause Clinics at the UNC Hospitals, and through the UNC Center for Women's Mood Disorders. Additionally, participants will be respondents to advertisements in local newspapers, social media, and mass email listservs seeking volunteers for research. To increase minority applicants, physicians who are African American or of other minority ethnic groups will be included as referral resources, and certain ads will particularly request minority volunteers.

5.2. Eligibility Criteria

5.2.1. Inclusion Criteria

To be eligible to participate in this study, an individual must meet all of the following criteria:

- Biologically female and 45 59 years of age based on self-report
- STRAW+10 reproductive staging criteria⁵⁹ for being in the early or late menopause transition based on self-reported bleeding patterns specifically menstrual periods of variable lengths and longer or shorter than premenopausal menstrual cycle lengths by seven or more days but no more than 12 months apart
- Negative screening mammogram within two years of enrollment based on screening mammogram results released to study personnel
- Body mass index between 18 45 kg/m2 measured by trained staff with professional scale in the laboratory during enrollment visit
- Moderate to severe irritability symptoms defined as a score of >10 on the ill temper scale of the Inventory of Depression and Anxiety Symptoms (IDAS)
- Emergence of, or increase in, irritability symptomatology concurrent with entering the menopause transition (defined by irregular bleeding patterns as defined above) based on self-report
- Experienced at least one very stressful life event (e.g., divorce, death of family member) within six months of enrollment based on self-report on the Life Experiences Scale.

5.2.2. Exclusion Criteria

Any individual who meets one or more of the following criteria will be excluded from participation:

- Use of psychotropic agents or hormonal preparations based on self-report.
- Use of herbal supplements (other than multivitamins) that are believed to affect mood or menopausal symptoms, such as St. John's Wort or black cohosh.
- Current suicidal intent or recent history of suicide attempts (within past 10 years) based on Mini International Neuropsychiatric Interview (MINI).
- A history of psychosis, bipolar disorder or substance dependence or active psychological symptoms severe enough to require treatment based on the MINI and a consensus diagnosis with co-Investigator, [name] (licensed Clinical Psychologist)
- A personal history of thrombophlebitis or thromboembolic disorders based on self-report with the Personal and Family History questionnaire (PFHQ)

- A personal or family history of cancer indicative of more than average risk (i.e., risk seen in the female population at large) for breast, ovarian or endometrial cancers based on self-report with The Personal and Family Cancer History Questionnaire. Specifically:
 - A personal history of breast, ovarian or endometrial cancer
 - Known BRCA mutation in self or first or second degree relative
 - A first degree relative with premenopausal breast cancer
 - o A first degree relative with ovarian cancer
 - o A first degree relative with endometrial cancer
 - A history of an abnormal breast biopsy indicative of precancerous cells
- Personal history of migraine with aura based on self-report and defined as
 - Focal neurological symptoms nerve-related functions or sensations, visual motor, or sensory
 - Changes in vision
 - 5-60 minutes before the pain begins
 - Vision blurred by flickering lights, spots, or lines
 - Unusual sensations
 - Pins and needles in one area of the body
 - Numbness in one area of the body
 - Other neurological
 - Difficulty talking
 - Sensitivity to light or sound
- According to JNC criteria, higher than stage 2 hypertension (systolic blood pressure ≥ 160 mmHg or
 diastolic blood pressure ≥ 100 mmHg) based on three stethoscopic blood pressures during quiet rest
 in the laboratory taken by trained personnel following the [name] laboratory blood pressure
 measurement protocol. Women whose blood pressure is being managed with a stable blood pressure
 regiment and meet BP inclusion criteria (Stage 2 hypertension or lower blood pressure (140-159 or
 90-99 mmHg)) will be included.
- Liver dysfunction or disease based on self-report with the PFHQ
- Undiagnosed abnormal genital bleeding based on self-report with the Side effects checklist (administered at baseline and at interim points in the protocol)
- A personal history of any cardiovascular disease including coronary artery disease, arteriosclerosis, heart attack, stroke based on self-report with the PFHQ
- Type I diabetes based on self-report with the PFHQ
- Known sensitivities to the matrix patch system in Climara® or allergy to peanut oil used in Prometrium® based on self-report with the PFHQ

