5. A history of E2 dependent neoplasia **6.** A history of liver dysfunction 7. A personal or family history suggesting elevated risk for E2-related cancer or thrombotic events 8. Use of psychotropics or hormonal agents **9.** A history of psychosis or bipolar disorder **10.** Suicidality with intent **11.** Current mood disorders of severity to require treatment A total of N = 50 eligible individuals will be enrolled. Based on our prior Numbers of Enrollees studies of TE2, of the estimated 50 women who pass our phone screening and come to an in-person enrollment, we predict that 30% (n=15) will not meet eligibility for TE2 after personal and family history review or will not meet reproductive staging criteria based on further detailed questions about their menstrual bleeding patterns. We anticipate that up to an additional 15% (n =5) may withdraw after enrollment, yielding 30 women who we anticipate will complete all aspects of the protocol and will have complete data. Up to 135 individuals will be recruited and screened. 40% will fail the screening for TE2 eligibility, and an additional 20% will not be interested in participating. Using a within-subjects, cross-over, placebo-controlled, double-blind Interventions or design, participants will be randomized (1:1) to either three weeks of **Exposures/Conditions** transdermal E2 (0.1 mg/day) or to three weeks of transdermal placebo as their first condition (Condition 1). Weekly mood ratings and daily ill temper (irritability) ratings will be collected across the three weeks. In week 3 of each Condition, daily E1G collections will commence (days 15-21) and the EEG session with Dot-Probe and Affective Posner Paradigm tasks will be administered (day 21). A three-week washout period will follow. Condition 2 (3 weeks) will follow the washout (placebo E2 if Condition 1 was active E2 or active E2 if Condition 1 was placebo) with identical assessments and timeline as for Condition 1. To prevent TE2-induced endometrial hyperplasia, 200 mg micronized progesterone/day for 10 days will be given to all women at study completion (Progesterone follow-up phase). **Outcome Measures** For Aim 1. Over the four-week baseline period, irritability symptoms will be measured daily using the III temper subscale of the Inventory of Depression and Anxiety Symptoms (IDAS). Urinary measures of E1G will be collected every other day (14 samples total) and assayed using an enzyme immunoassay (Arbor Assays, Ann Arbor, MI), with sensitivity at < 22.5 pg/mL to calculate within subject fluctuation in E1G (indexed by the standard deviation of E1G over the four weeks). At the end of baseline week 4, Theta and Beta oscillatory frequencies will be assessed at rest and in response to the Dot Probe task which measures attention bias to angry faces (threat attention bias) and in response to the Affective Posner Paradigm that measures relational aggression (approach behavior) in response to frustration. For Aim 2. The outcomes are identical to those in Aim 1. The primary comparison will be within subject - comparing the active TE2 condition

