In sum, the Endocrine Society concludes that "Data from the various Women's Health Initiative studies, which involved women of average age 63, cannot be appropriately applied to calculate risks and benefits of menopausal hormone therapy in women starting shortly after menopause." ⁵⁰In fact, there is substantial evidence for the safety of E2, particularly if administered to women within 10 years of their final menstrual period and if administered as the transdermal form (e.g., lower risk of VTE). ^{50,54,55} Given our plans to administer transdermal E2 to women: 1) for only 3 weeks, 2) no older than 55 years of age, 3) who are still menstruating, albeit with variable cycle lengths, and 4) who are at no greater than average risk for CVD, breast cancer or VTE, the risk of serious adverse events is exceedingly low.

Psychological Risks: The structured interviews to assess current and lifetime psychiatric illness and suicide ideation and behavior and the Life Events survey may be associated with some psychological distress. Some items in the questionnaires may provoke some negative emotion in some individuals. There is also the risk a woman will experience the onset of a clinically significant affective episode, worsening of affective symptoms over the course of the 13-week protocol that would go undetected or untreated. There is the risk for emergent suicide ideation with intent or suicide attempts. However, importantly, there is no evidence that asking about suicidality increases suicidality—it actually tends to reduce it.⁵6However, because we are excluding women with past suicide attempts (the strongest predictor of future attempts) and excluding those at enrollment with any current suicide ideation with intent, combined with the requirement that suicide ideation (without intent) at enrollment be of low frequency and duration, the chance that suicide intent or behavior will emerge over the course of the 13 week study is remote. One third of Americans endorse suicide ideation at some point in their lives, ⁵⁷ yet less than 0.01% die by suicide each year. Because women in the MT are at increased risk for both ideation and attempts, ⁵⁸ we will include women with current suicide ideation if it is of mild severity (no intent) and limited frequency and duration (≤ once/week; < 1 hour/episode) as it does not predict imminent risk for a suicide attempt (in the absence of a history of multiple attempts).

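### Section 12.2 calls suicide risk remote on the strength of exclusions that Section 5.2.2 carries only in part: attempts are excluded for 10 years only, and the ideation limit is not listed

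*Combined protocol and SAP*

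**What the plan says.** Section 12.2 (Risk / Benefit Assessment) concludes that "the chance that suicide intent or behavior will emerge over the course of the 13 week study is remote". It argues this from who is let in. First, "we are excluding women with past suicide attempts (the strongest predictor of future attempts"), with no time window. Second, current ideation with intent is excluded at enrollment. Third, there is a "requirement that suicide ideation (without intent) at enrollment be of low frequency and duration". The same paragraph then gives this as a rule: "we will include women with current suicide ideation if it is of mild severity (no intent) and limited frequency and duration", with bounds of once a week or less and under 1 hour per episode. It adds that such ideation does not signal imminent risk provided there is no record of multiple attempts.

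Section 5.2.2 (Exclusion Criteria) has one suicide criterion: "Current suicidal intent or recent history of suicide attempts (within past 10 years) based on Mini International Neuropsychiatric Interview (MINI". A separate criterion excludes "active psychological symptoms severe enough to require treatment based on the MINI and a consensus diagnosis". The synopsis list has only "Suicidality with intent".

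On a smaller matter, reason 5 in Section 7.2 for not requiring a gynecological exam is that every participant is in the early transition with semi-regular periods. The synopsis and Section 5.2.1 admit early or late transition, with periods up to 12 months apart. Section 12.2 gives an upper age of 55 where 5.2.1 gives 59, and Section 9 describes recruits as early-transition only.

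**The concern.** The risk assessment and the eligibility list describe different populations. Screening staff are likely to work from 5.2.2, whereas anyone judging whether the risk is acceptable reads 12.2. If 5.2.2 is followed to the letter, women can be enrolled whom 12.2 counts as kept out, and its conclusion then rests on protections that the screening criteria do not provide.

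The population makes this worth settling. Section 12.2 itself says women in the menopause transition are at increased risk of ideation and attempts, and it names past attempts as the strongest predictor of future ones. Entry requires an ill temper score above 10 and a very stressful event in the previous six months. Section 2.2 cites evidence that stopping transdermal estradiol raises depressive symptoms within one week in women with past perimenopausal depression, and the crossover takes every completer off estradiol once.

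The stake is participant safety and the accuracy of the risk statement. The estimand, analysis, power and randomization are not touched.

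**Working it through.** No arithmetic is needed. The check sets each ground in 12.2 against the criteria used for screening.

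| Ground in 12.2 | Section 5.2.2 | Synopsis list | Carried into 5.2.2? |
|---|---|---|---|
| Past attempts excluded, no time limit | Only attempts within 10 years | Not listed | In part |
| Ideation with intent excluded | Current intent excluded | Listed | In full |
| Ideation without intent limited to once a week or less, under 1 hour per episode | Not listed | Not listed | No |

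Of three grounds, one is carried in full, one in part and one not at all.

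Next, take three women, each without current intent and without symptoms that the consensus diagnosis finds to need treatment.

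- **One attempt, more than 10 years ago.** No criterion in 5.2.2 applies. The first ground in 12.2 treats her as excluded.
- **Several attempts, all more than 10 years ago, with mild infrequent ideation now.** No criterion in 5.2.2 applies. The proviso in 12.2 about multiple attempts is not met, so its reassurance about mild ideation does not extend to her.
- **Ideation without intent more often than once a week.** No criterion in 5.2.2 applies. The rule in 12.2 would keep her out.

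Then take the safeguards in turn.

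- Excluding symptoms that need treatment may remove some women with frequent ideation. It is a clinical judgment without a frequency or duration threshold, and it concerns current symptoms, so an old attempt does not trigger it.
- Under Section 4.3 an investigator will "review each MINI with the research staff member who conducted the interview to determine a consensus diagnosis". This improves ascertainment, but the reviewer still applies the criteria as listed.
- CES-D suicide items and total score are reviewed weekly (Sections 4.3 and 7.8), and Section 12.5 has staff watch the IDAS suicide subscale. As on-study monitoring these detect deterioration after entry; they do not define who enters.

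None makes an older attempt an exclusion, and none puts the ideation limit into 5.2.2.

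For the exam waiver, reason 5 is untrue for late-transition women, whom 5.2.1 admits. The 7-day figure in reason 5 may be shorthand, since Section 5.3.2 uses the same figure for the qualifying variance, but the early-stage premise still does not fit them.

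**The case against.** The best reply is that the ideation rule is not missing from the protocol. Section 12.2 states it as an enrollment requirement with thresholds, and suicidality is assessed at enrollment with the MINI. Staff who follow the whole document would not enroll a woman above the limit. That stands: a reader might infer that the protocol has no ideation limit, and the documents do not support this. The gap is that the limit is absent from the list used for screening.

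It can also be said that 12.2 is not a lifetime ban when read to its end, because the proviso about multiple attempts contemplates some attempt history, and that the 10-year window in 5.2.2 looks deliberate. This too has force. A reader might infer that every past attempt must be excluded; the documents do not show that, and it is a clinical trade-off for the sponsor. But the proviso cuts both ways, because 5.2.2 does not exclude multiple attempts older than 10 years.

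Two further inferences should be resisted. The share of adult life outside the 10-year window counts years, not attempts, and measures no risk. And the CES-D item trigger in Section 7.8 being higher than the entry limit in 12.2 is not a contradiction: one prompts review during the study, the other governs entry.

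On the exam waiver, a reader might infer that late-transition women are left unprotected. They are not. Reasons 1 to 4 apply to both stages, the ultrasound trigger for prolonged or profuse bleeding has no stage limit, cancer history and undiagnosed abnormal bleeding are excluded, estradiol exposure is three weeks, and all women receive progesterone. This is a wording correction, as are the age and Section 9 points.

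**Conclusion.** The inconsistency is real and should be corrected. The conclusion of remote suicide risk in 12.2 rests on three grounds, of which 5.2.2 carries one in full, one in part and one not at all. Its proviso about multiple attempts is also unsecured for attempts more than 10 years old. Existing safeguards reduce the gap without supplying the missing exclusions.

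The number of women affected cannot be estimated, since the documents give no rates of past attempts or of ideation in this population. The finding assumes only that 5.2.2 is the list staff screen from. It does not show that the actual risk is other than low, only that the stated argument for it does not match the stated criteria. The points on 7.2, the age of 55 and Section 9 are minor and change no conclusion.

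**What to change.** 1. Add the ideation limit from 12.2 to 5.2.2 as an explicit exclusion: ideation without intent that occurs more than once a week or lasts 1 hour or more per episode.
2. Make the attempt rule agree. At minimum, restate 12.2 to say that attempts within the past 10 years are excluded, and re-argue the conclusion of remote risk on that basis, dealing expressly with multiple attempts more than 10 years old. Alternatively, the sponsor may exclude all past attempts in 5.2.2 and leave that ground in 12.2 as it is.
3. Minor wording: change reason 5 in 7.2 to early or late transition as defined in 5.2.1, with the study gynecologist confirming that the waiver still applies; change 55 to 59 in 12.2; and state in Section 9 that both stages are eligible.

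The cost is amendment wording and one confirmation by the gynecologist. The MINI is already given at enrollment, so no visit or analysis is added. Excluding all past attempts would cost some screen failures; keeping the 10-year window avoids them.
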